## **Procedures:**

Blood Transfusion: Participants will receive either 1 or 2 packed RBC units as ordered by their attending physician. Units will be infused intravenously via programmable electronic infusion pump (Baxter, Inc) over 1 hour per unit. The subjects will receive only cross-matched leukoreduced units. No pre-medication will be permitted. Subjects will be monitored closely for any reactions during transfusion following standard hospital policy. In the event that blood units of the prespecified age are not available, patient will receive their clinically indicated transfusion with blood units of any age per hospital protocol. This would be considered a protocol deviation and those patients will then be excluded from the study

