Up to now, prospective mechanistic investigations of the effects of saRBC transfusions on human recipients have been limited to either hospitalized subjects or healthy volunteers ENREF\_14(preliminary data). The use of inpatient subjects is complicated by the fact that they are often critically ill with complex and dynamic medical conditions, their transfusion needs are unpredictable and heterogeneous. In contrast, with healthy volunteers, the timing and volume of study transfusions can be controlled. However, healthy volunteers cannot ethically have their hematocrits reduced to levels seen in anemic hospitalized patients, nor do they typically have underlying endothelial dysfunction seen in hospitalized patients, which may synergize with the effects of saRBC transfusions to further reduce NO bioavailability. Thus, while both groups have been used successfully to study the effects of fresh vs. saRBC transfusions, each study population has limitations. Ideally, investigations of the vasoinhibitory effects of saRBCs would best be performed in anemic patients who have predictable, repetitive transfusion requirements such that a cross-over transfusion design can be used to control for inter-individual heterogeneity. At Emory, we care for a large population of chronically anemic patients who require outpatient blood transfusions every 2 to 4 weeks for thalassemia, aplastic anemia, myelodysplastic syndrome and other disorders. Thus, the second important component of the proposed studies will be the recruitment of these patients as study subjects: they have relatively stable disease-related anemias and vascular dysfunctions, are transfusion-dependent and can be randomized into a cross-over study design to receive fresh transfusions during one visit, and saRBC transfusions during the next (or vice versa). The proposed studies will test our hypothesis that transfusion of saRBCs (day 21-42 of storage), but not fresh RBCs (< 10 days), will impair NO-mediated vasodilation and also reduce exercise tolerance and oxygen carrying capacity in an ambulatory transfusion-dependent adult population. **The Specific Aims are:**

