**Impaired FMD responses in hospitalized patients transfused with saRBCs but not fresh RBCs.** As a extension of the *in vitro* aortic ring assays, and as part of a larger NIH funded investigation into the adverse effects of saRBC transfusions, we have also successfully studied the vascular effects of fresh RBCs vs. saRBCs on inpatients receiving medically indicated blood transfusions for anemia. After informed consent, subjects were randomized to receive either a fresh (<10 days old) or aged (>21 days old) blood transfusion. Endothelial function was assessed by FMD of the brachial artery prior, during, 1 hour after, and 24 hours following transfusion. Data were analyzed using a linear mixed effects model.

The 45 subjects who have completed the study had a mean age of  $58.5 \pm 13$  (SD). 52% were male and 50% were white. There were no differences in demographics, CVD risk factors, known CVD, amount of RBCs transfused, or baseline FMD between groups. Mean age of RBC units was  $9.1 \pm 3.1$  days and  $29.8 \pm 5.7$  days in the fresh and saRBC groups, respectively. As compared to pretransfusion FMD results, patients receiving fresh RBCs had no significant change in FMD at any time point either during or after transfusion ( $p > 0.05$ ; Fig 3, black bars). In a marked decrease at 1 hour post-transfusion (which did not reach statistical significance,  $p > 0.05$ ); however, by 24 hours after transfusion the continued reduction in FMD was statistically significant ( $p = 0.037$ ; Figure 3, white bars; manuscript in preparation). These inhibitory effects of saRBCs, but not fresh RBCs, on NO-mediated vasodilation in hospitalized patients are consistent with our *in vitro* studies shown above (Figs 1 and 2), further supporting the INOBA hypothesis. Unlike recently published reports which found no vascular effects of either fresh or saRBC transfusions in healthy recipients, we studied ill, anemic patients receiving standard allogeneic transfusions, thus underscoring the likely importance of recipient factors to adverse effects of saRBC transfusion.

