## EXPERIMENTAL DESIGN AND METHODS

## **Rationale:**

In our preliminary studies, we demonstrated that saRBCs (but not fresh RBCs) impair NO-mediated vasodilation when studied using *in vitro* models as well as in hospitalized transfusion recipients. Some limitations of studying transfusion outcomes in hospitalized patients include the heterogeneity of this population, unpredictable times of transfusions, urgent/emergent circumstances, and a lack of standardization of inpatient covariates including time of day, diet and other associated therapies. Vascular tests (FMD and PAT) and measures of circulating NO, oxidative stress and inflammation are sensitive to co-morbidities, diet and medications. Finally, dynamic changes in patients' condition can also potentially confound experimental results. Conversely, transfusion studies can be performed in healthy volunteers. However, these subjects rarely have underlying endothelial dysfunction (which may synergize with saRBCs and magnify their effects on NO bioavailability) and for ethical reasons cannot be rendered anemic or transfused with allogeneic blood. Thus, transfusion effects in healthy volunteers may not necessarily be reflective of outcomes seen in sick patients.

In order to overcome these limitations, and to investigate the relationships between blood storage, reduced NO bioavailability, impaired vasodilation, and physiologic outcomes of transfusion, we propose to investigate the effects of saRBC transfusions in a chronically transfusion-dependent but ambulatory population. This approach has the following advantages: 1) these patients are stable over the course of days to weeks, 2) studies are performed under conditions of controlled diet, circadian rhythms, medications, etc., 3) the same subject receives both fresh and saRBCs in a randomized cross-over study design (see schema in Fig 4), and 4) because these patients are ambulatory, they can undergo cardiopulmonary exercise testing. Successful completion of the proposed studies will advance our understanding of mechanisms underlying the adverse events and functional consequences of saRBC transfusion and validate a model for subsequently evaluating potential treatments and storage techniques to reverse saRBC-mediated impairments (the latter objectives are beyond the scope of the present investigations).

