**Subject Population:** Twenty-four subjects diagnosed with stable transfusion dependent anemia will be recruited and undergo a screening health questionnaire and physical examination to ensure eligibility. All subjects will provide informed consent prior to entry into the study. We will recruit adult subjects without preference to any race, gender or socioeconomic status. [name] translational research group in the Department of Cardiology regularly enrolls patients into clinical studies, and has experience consenting patients, randomizing them to study arms, and performing study protocols including the use of these non-invasive assays. This clinical research team oversaw execution of the clinical study comparing fresh vs. saRBC transfusions in hospitalized patients described in the preliminary results. Furthermore, we have also consulted with our Hematology colleagues, and have identified a large number of potential subjects who fit our criteria for this study. The proposed study has been approved by the Emory IRB.

**Eligibility Criteria:** Male or female volunteers age 21-80 with any condition resulting in RBC transfusion-dependent anemia will be eligible to participate. Participants may receive either 1- or 2-unit transfusions as required clinically so long as their transfusion requirement is stable throughout the study period.

**Ineligibility Criteria:** Age <21 or > 80 years, pregnancy, acute infection in previous 4 weeks, active substance abuse within the past year, inability to give informed consent, inability to return for follow-up or the presence of alloantibodies that would limit the blood bank's ability to obtain correctly aged RBC units. Participants with contraindications to cardiopulmonary exercise testing may be allowed to participate in the other study aims.

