**Study Design:** Studies will be performed in a temperature-controlled vascular laboratory in the outpatient unit of the Clinical Research Network, ACTSI, at Emory University Hospital after an overnight fast. After providing informed consent, subjects will be randomized to receive their next clinically-indicated outpatient transfusion with fresh (<10 days old) blood or storage-aged (>21 day old) blood. Following their first transfusion, subjects will be crossed-over to receive the opposite aged product. Subjects and individuals conducting and interpreting experimental tests will be blinded to the age of RBC units. To maintain safety, clinical staff will not be blinded. All subjects will receive clinically indicated transfusions with cross-matched, leukoreduced AS1 units of packed RBCs from available blood bank inventory. The effects of RBC transfusion on blood flow and peripheral O2 delivery will be directly tested in the 24 volunteers using non-invasive assessments of endothelial function including: brachial artery flow-mediated dilation (FMD) and pulsatile arterial tonometry (PAT). Symptoms of fatigue and anemia will be objectively assessed at every visit using the self-administered FACT-An questionnaire (Functional Assessment of Cancer Therapy – Anemia). Vascular function will be assessed prior to transfusion as well as 1 hour and 24 hours after blood transfusion. Concurrently, subjects will undergo cardiopulmonary following each transfusion. Blood samples will be obtained at baseline, prior to and following each transfusion and from each unit transfused to perform metabolic marker testing.

**Study Schedule (Figure 4, below):** Each subject will be studied over a total of 4 visits, as shown in the Figure and described below.

**Screening:** Subjects will be screened with history and physical for inclusion and exclusion criteria and provide written consent. Subjects to meet inclusion and exclusion criteria, and give consent, will be randomized into either Group A or Group B.

**Visit #1 (Transfusion #1):** Subjects will return fasting to receive a scheduled, clinically-indicated RBC transfusion. Depending on their randomization to Group A or B, they will receive either fresh or saRBCs; an infusion pump will be used to administer the blood over a 1 hour period. FMD and PAT and will be performed and blood samples will be obtained for measurement of oxidative stress and other metabolic markers prior to and 1 hour following RBC transfusion.

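### Subjects already randomized are excluded when blood of the allocated age is out of stock, although moving that period to their next transfusion, 2 to 4 weeks later, would keep most of them

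*Combined protocol and SAP*

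**What the plan says.** The shortage rule is in the Blood Transfusion paragraph under Procedures. If units of the prespecified age cannot be had, the "patient will receive their clinically indicated transfusion with blood units of any age per hospital protocol". The consequence follows: "This would be considered a protocol deviation and those patients will then be excluded from the study".

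Other parts of the protocol that bear on this rule:

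- **Study Design.** Randomization follows consent and precedes the first study transfusion, so the exclusion is always after randomization. Each subject needs both products, on two occasions. Units are "packed RBCs from available blood bank inventory"; no reserved supply is described.
- **Ineligibility Criteria.** Patients are not enrolled if alloantibodies would limit the blood bank's "ability to obtain correctly aged RBC units". This is the only step aimed at shortage before enrollment.
- **Specific Aims, introduction.** The source population is "chronically anemic patients who require outpatient blood transfusions every 2 to 4 weeks".
- **Subject Population and Statistical considerations.** Twenty-four subjects are recruited, and both sample size paragraphs use 24.
- **Time table.** Enrollment covers the first 18 months.

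No section provides for deferring or repeating a period, replacing an excluded subject, or enlarging the sample for losses.

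**The concern.** The rule has a sound purpose: a subject given blood of the wrong age does not contribute to the fresh versus stored contrast. But it removes the subject from the trial, when only that day's transfusion is unusable. In a crossover of 24, each exclusion costs one within-subject comparison, for a reason that concerns the blood bank's stock and not the patient.

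The population was chosen because its transfusions are predictable and repeated, so a missed period can be rescheduled at the next visit. The plan does not use that advantage. At stake are precision, and the subject's effort if the shortage comes at the second transfusion, when the first period's vascular tests, exercise test and blood samples are done.

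**Working it through.** **1. Inputs.** From Statistical considerations, Aim 2: n = 24, difference 130 ml/min, SD 190, two-sided alpha 0.05, Wilcoxon test, stated power 86%. Aim 1: paired t-test, n = 24, two-sided alpha 0.05, power 0.8, SD 3.11%, detectable change 0.85%, observed change 2.4% with stored blood in inpatients. I take 190 as the SD of the paired difference; the plan does not say so, but its own figure reproduces on that reading.

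**2. Aim 2, stated figure.** Noncentral-t power for paired data, with n multiplied by the Wilcoxon efficiency 3/π:

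- Effective n = 24 × 3/π = 22.92.
- Noncentrality = (130/190) × √22.92 = 3.28.
- Power = 87.9%. With effective n rounded down to 22 it is 86.4%, which matches the stated 86%. A simulated exact signed-rank test gives 88%.

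**3. Aim 2 power if excluded subjects are not replaced.** Same method:

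| Completers | Effective n | Noncentrality | Power |
|---|---|---|---|
| 24 | 22.92 | 3.28 | 87.9% |
| 22 | 21.01 | 3.14 | 84.7% |
| 20 | 19.10 | 2.99 | 80.7% |
| 19 | 18.14 | 2.91 | 78.5% (78.47%) |

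Power goes below 80% at the fifth loss. These figures count supply losses only.

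**4. Aim 1.** At n = 24, 80% power needs a standardized change of 0.597. With the stated SD the detectable change is 0.597 × 3.11 = 1.86%, not 0.85%. To detect 0.85% the SD of differences would have to be 0.85/0.597 = 1.42%, which the plan does not give. The loss therefore depends on which inputs are believed:

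| Change, SD of differences | n = 24 | n = 22 | n = 20 | n = 19 |
|---|---|---|---|---|
| 0.85%, 1.42% (implied) | 80% | 76% | 72% | 69% |
| 0.85%, 3.11% (stated) | 25% | 23% | 21% | 20% |
| 2.4%, 3.11% (both stated) | 95% | 93% | 91% | 89% |

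Every row falls as subjects are lost, but no row can be put forward as the Aim 1 result.

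**5. Expected completers.** Let q be the probability that units of the allocated age are missing at a study transfusion. The documents do not give q; it is assumed, and taken as independent between transfusions.

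- Present rule: 24(1 − q)².
- One deferral allowed per period: 24(1 − q²)².
- Two deferrals allowed per period: 24(1 − q³)².

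| Assumed q | Exclusion | One deferral | Two deferrals |
|---|---|---|---|
| 2% | 23.0 | 24.0 | 24.0 |
| 5% | 21.7 | 23.9 | 24.0 |
| 10% | 19.4 | 23.5 | 24.0 |
| 20% | 15.4 | 22.1 | 23.6 |

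If excluded subjects were replaced instead, 24 completers would need 24/0.95² = 26.6, so 27 randomized at q = 5%, and 24/0.90² = 29.6, so 30 at q = 10%.

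**The case against.** The strongest objection is that no loss has been shown. No shortage rate is given, the transfusions are scheduled, patients with problem alloantibodies are screened out, and nothing says that units are not already requested in advance. If subjects are replaced, on which the plan is silent, power is kept and the cost is wasted visits. All of this stands, and it is why the point is a modest one.

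Deferral is also a trade-off. The Rationale claims stability over days to weeks. One deferral of period 2 widens the gap between the study products from 2–4 to 4–8 weeks and puts a transfusion of uncontrolled age between them. The exercise test is done only after transfusion, so VO2Max has no pre-transfusion value to absorb drift. This stands in part. The transfusion before Visit 1 is of uncontrolled age too, and FMD is measured before each study transfusion. For VO2Max the objection is a reason to cap deferrals and re-check stability, not a reason to exclude.

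A reader might infer more than the documents support:

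- **That shortage has already occurred.** In Preliminary Data, inpatient "subjects were randomized to receive either a fresh (<10 days old) or aged (>21 days old) blood transfusion", yet fresh units are reported at 9.1 ± 3.1 days, a spread hard to fit below 10. Even if a unit was out of window, nothing shows that shortage was the cause. That study faced "unpredictable times of transfusions, urgent/emergent circumstances" and says nothing about frequency here.
- **That first-period data are thrown away.** The rule says only that the patient is excluded from the study; whether completed measurements stay in the mixed model is not stated.
- **That having one of two units in window triggers exclusion.** Partial supply is not addressed.
- **That the exclusions bias the treatment effect.** Stock shortage is unlikely to depend on the outcome, and nothing in the plan suggests that it does.

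**Conclusion.** The concern holds as an avoidable loss of precision. The plan drops randomized subjects for a supply reason, in a population where the affected period could usually be repeated at the next transfusion, and it makes no provision for the loss.

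The size is conditional. If exclusions are not replaced, two to five of them take Aim 2 from about 88% to between 85% and 78%. At an assumed shortage of 5% to 10% per period, one permitted deferral keeps about 2 to 4 more subjects (23.9 − 21.7 = 2.2; 23.5 − 19.4 = 4.1). Aim 1 loses power as well, but because its 0.85% and its SD of 3.11% do not agree, that loss should not be quoted as a single percentage.

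The conclusion rests on three assumptions: 190 is the SD of the paired difference, shortages are independent between transfusions, and matching units become available later while the transfusion requirement stays stable.

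**What to change.** In the Blood Transfusion paragraph under Procedures, replace the exclusion sentence with wording such as:

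> If units of the allocated age cannot be supplied, the subject is transfused off study as clinically indicated and that study period moves to the next scheduled transfusion, with at most two deferrals per period and a re-check that the transfusion requirement is still stable. Completed period data are kept, and the deferral and the age of the off-study units are logged.

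Each deferral costs a delay of 2 to 4 weeks, which an 18-month enrollment period can usually absorb, and the subject's transfusion need must stay stable for that much longer. A deferred second period brings an off-study transfusion between the two study products. This matters most for VO2Max, so the logged unit age should be available when that endpoint is interpreted. Clinical care and the planned mixed model do not change.

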### **Study Measurements:**

Endothelial function assessment -- Brachial artery flow-mediated vasodilation (FMD): All studies will be performed in a temperature-controlled vascular laboratory after an overnight fast. The brachial artery of the non-dominant arm will be imaged using a high-resolution 13 MHz ultrasound transducer (Acuson) as previously described in detail and as used for the studies shown in Fig 3 of the preliminary results section. Briefly, a blood pressure cuff on the forearm will be inflated to supra-systolic pressures to produce 5 minutes of ischemia. On cuff deflation, reactive hyperemia produces an acute increase in shear stress with an accompanying release of NO. Imaging of the brachial artery is performed continuously for the next 120 seconds, providing the data necessary to calculate flow-mediated dilation. After a 10 minute recovery interval, sublingual nitroglycerin will be given (0.4 mg) and the brachial artery will be re-imaged after 3 minutes. Image analysis will be performed by an experienced FMD investigator who is blinded to the treatment arm. Arterial diameter will be measured using a validated proprietary software program (Medical Instruments Inc.). Brachial artery FMD will be calculated as [(postischemia diameter - baseline diameter) / baseline diameter] X 100.

Reproducibility: FMD is well-accepted technique. In our laboratory, the mean difference in FMD (%) between 2 consecutive assessments performed in 11 subjects an average of 8 days apart was 1.26% ( $\pm 0.76\%$ ,  $r=0.75$ ). The mean difference in the FMD (%) between 2 readings of the same 11 measurements was 0.82% ( $\pm 0.48\%$ ,  $r=0.97$ ). (unpublished data)

Endothelial function assessment – Reactive Hyperemia Index (RHI) as measured using Pulsatile Arterial Tonometry (PAT, Itamar Medical Ltd.): This assay uses a device that measures reactive hyperemia of the finger. The magnitude of hyperemia correlates with coronary microvascular endothelial function, peripheral vascular endothelial function measured as brachial reactivity, and can be inhibited by LNG monomethyl arginine, indicating that it is NO-dependent. We are employing this technique currently in our catheterization lab population and have found it to be easy to use and reproducible.

Technique: Subjects will be studied in the supine position in a temperature-controlled room. Baseline blood pressure of both hands is measured and PAT probes are placed one on each hand at the same finger (fingers 2, 3 or 4). Following a 10 min. equilibration period, the blood pressure cuff is inflated to 60 mmHg above systolic pressure for 5 minutes followed by deflation of the cuff while the pulsatile recordings from both study and control fingers are measured.

Cardiopulmonary Exercise Testing (CPX): Graded treadmill exercise testing will be performed following American Heart Association guidelines using the Modified Balke protocol. A treadmill with full metabolic cart (Carefusion INC, USA) will be used for CPX. Testing measurements will include 1) Maximal oxygen uptake (VO2Max): This is the Primary Endpoint of Aim 2 and is defined as the value achieved when VO2 remains stable despite a progressive increase in the intensity of exercise. This is synonymous with peak aerobic capacity. Secondarily, CPX will report: 2) Respiratory exchange ratio (RER): Related but not equivalent to its cellular counterpart, the respiratory quotient, RER is defined as the ratio of VCO2 to VO2. 3) O2 pulse: The amount of O2 consumed from the volume of blood delivered to tissues by each heartbeat; this index is calculated as: O2 pulse = VO2 / heart rate. 4) Peak VO2lean: the peak oxygen uptake adjusted for lean body mass. Reported as a lean body weight-adjustment parameter in mL/kg per minute. These data are then integrated with heart rate, blood pressure, work rate, electrocardiography findings, and the occurrence of any clinical symptoms for a comprehensive analysis of exercise tolerance before and after transfusion.

Blood Testing: Biomarkers of oxidative stress (glutathione/glutathione disulfide and cysteine/cystine redox potentials) are measured in an Emory University Core Lab directed by [name], and available for use by all Emory investigators. [name] is an internationally recognized expert in the area of glutathione (GSH) and cysteine metabolism, and has substantial experience with measurements of reactive oxygen species. He has optimized HPLC methods for quantitation of oxidative stress markers. NO metabolites (nitrate, nitrite, and nitrosylated hemoglobin and thiol) levels will be measured in [name] laboratory at Emory (see support

letter). 2,3-DPG, plasma free hemoglobin and inflammatory marker levels will be measured in [name] laboratory.

